1. SYNOPSIS

Study Title	Investigating non-invasive brain stimulation to enhance fluency in people who stutter
Internal ref. no. / short title	INSTEP Trial
Study Design	Double-blind randomised controlled trial. Active treatment: bi-hemispheric tDCS, Control: Sham tDCS. Minimisation randomisation.
Study Participants	Healthy adult males with developmental stuttering and healthy male controls with no speech disorders
Planned Sample Size	70 (40 participants with developmental stuttering, 30 control participants)
Planned Study Period	1 st November 2017 – 30th April 2020
	Outcome Measures
Primary	Change from baseline (i.e. baseline subtracted) in a clinical measure of stuttering severity (SSI-4), post training (1 week, 6 weeks, and 3 months after training).
Secondary	Change from baseline (i.e. baseline subtracted) in: (i) % disfluent syllables produced during conversation; (ii) % disfluent syllables produced during reading post training (1 week, 6 weeks, and 3 months after training). (iii) total score on an attitudinal measure (OASES), post training (6 weeks, and 3 months after training).
Other Pre-specified	Change from baseline (i.e. baseline subtracted) in: (i) total score on the Premonitory Awareness in Stuttering Scale; (ii) total score on the Beck Anxiety Inventory; (iii) subjective and objective ratings of stuttering severity and naturalness, post training (1 week, 6 weeks, and 3 months after training). Changes from baseline (i.e. baseline subtracted) % disfluent syllables produced during (i) conversation and (ii) reading, during the 5-day training (immediately post intervention days 1 to 5; immediately pre-intervention days 2 to 5).
	Exploratory (non-behavioural) measures
Other	We will use MRI and TMS, to evaluate neural structure, function, and excitability in people who stutter and in healthy controls. Using MRI, we will also obtain images of the vocal tract during speech. These measurements will be obtained just before training begins and 1 week after the end of the training in people who stutter and once only in healthy controls.

2. ABBREVIATIONS

BAI	Beck Anxiety Inventory
CI	Chief Investigator

DS	Developmental Stuttering
fMRI	Functional magnetic resonance imaging
GCP	Good Clinical Practice
ICF	Informed Consent Form
IDREC	Interdisciplinary Research Ethics Committee
MRI	Magnetic Resonance Imaging
OASES	Overall Assessment of Speaker's Experience of Stuttering
OHBA	Oxford Centre for Human Brain Activity
PAiS	Premonitory Awareness in Stuttering Scale
PI	Principal Investigator
PIS	Participant/ Patient Information Sheet
PWS	People who Stutter
REC	Research Ethics Committee
rsfMRI	Resting state functional magnetic resonance imaging
SOP	Standard Operating Procedure
SSI-4	Stuttering Severity Instrument, 4 th Edition
TCS	Transcranial Current Stimulation
tDCS	Transcranial Direct Current Stimulation
TMS	Transcranial Magnetic Stimulation

3. BACKGROUND AND RATIONALE

Developmental stuttering is a disorder affecting the fluency of speech, characterized by repetitions or prolongations of sounds and frequent hesitations or pauses. It affects 5% of children and persists to adulthood in about 1%. Changing the way speech is produced in adults who stutter is a particular challenge for speech and language therapy and there is a need for novel interventions, therefore. One such intervention involves the application of transcranial direct current stimulation (tDCS) alongside speech therapy. tDCS influences brain activity by modulating neuronal plasticity through the application of weak electrical currents across the brain. Pairing tDCS with speech therapy has potential for producing larger or longer lasting effects and reducing time spent in therapy. In a previous study, we showed that a five-day training regime of anodal tDCS combined with temporary fluency enhancers led to improvements in speech fluency in PWS that were sustained for five weeks post intervention.

The first aim of our study is to replicate our previous finding using a slightly different form of tDCS combined with speech fluency training to improve outcomes in people who stutter (PWS). We will use metronome-timed speech to temporarily induce fluency during the training. PWS will have this training for 40 minutes a day while receiving anodal tDCS over the left frontal cortex and cathodal tDCS over the right frontal cortex for five consecutive days (1mA for 20 mins at the start of the intervention on each day) in a double-blind randomized controlled trial. Outcomes

will be measured in terms of changes to stuttering severity, dysfluency rates for reading and conversation, naturalness ratings, and attitudes to stuttering.

The second aim of our study is to understand how changes in the interactions between sensory and motor regions of the brain relate to changes in speech fluency in PWS. We will use MRI to measure brain structure and function. We will also image the vocal tract during speech production. Transcranial magnetic stimulation (TMS) will evaluate changes in excitability of the motor system underlying speech production. These studies are exploratory measures of the intervention in PWS.

4. STUDY DESIGN

This is a double-blind, placebo-controlled (sham tDCS), randomised trial, with 20 participants with developmental stuttering recruited for each arm of the trial. The participants will be expected to complete at least two visits to the OHBA imaging centre in Oxford (at baseline and at the +1 week follow up) for the assessments of neural structure, function, and to assess movements of the vocal tract (MRI, TMS, & vocal tract imaging). In addition, participants will complete one live interaction and one videoconference at baseline and at +1 week follow up, complete training for 5 days, and engage in two more videoconference interactions for follow-ups (6 weeks and 3 months after the end of training), which will involve doing reading and conversation tasks so speech fluency can be assessed. The researchers can travel to the participant's home or office for the live components of these visits as well as the tDCS + speech fluency training. In total, participants will have 9 visits over a 5-month period. A flowchart illustrating the study design is included in Appendix A.

5. PARTICIPANT IDENTIFICATION

5.1. Study Participants

Adult male participants with developmental stuttering of mild-moderate severity (as ascertained by a total score of greater than 20 on the stuttering severity instrument – version 4 [SSI-4]) and healthy male volunteers aged 18-45 years.

5.2. Inclusion Criteria

- Participant is willing and able to give informed consent for participation in the study.
- Male, aged 18 years or above.
- Diagnosed with developmental stuttering of mild-moderate or greater severity
- Native speaker of English
- Normal or corrected-to-normal vision
- Normal hearing

5.3. Exclusion Criteria

The participant may not enter the study if ANY of the following apply:

- Speech, language or communication disorder other than developmental stuttering.

- Contraindication to brain stimulation (tDCS or TMS)
- Contraindication to MRI
- History of drug abuse
- History of a neurological or psychiatric illness
- Any previous neurosurgical procedures
- Taking prescription or over-the-counter medication that may affect brain function (for example, anti-depressants)
- Family history of epilepsy (first degree relative)
- Severe claustrophobia (as they may be unable to tolerate scanner)

The inclusion and exclusion criteria for **the control group** of participants are as above, with the exception that developmental stuttering will be an exclusion criterion.

6. STUDY PROCEDURES

6.1. Recruitment

Volunteers who self-report stammering/ stuttering will be recruited for the study, in addition to an age- and gender-matched control sample.

We will advertise the study within the university through traditional channels, for instance, on departmental mailing lists and posters located in University Departments (including at Oxford Brookes), social media channels, to the departmental participant pool, as well as on noticeboards in colleges affiliated with the University. We will also place advertisements in the local community (e.g. in community centres, sports centres etc.). In addition, we will recruit through self-help and advocacy groups for people with stammering, such as the British Stammering Association. With their permission, we will post advertisements in their newsletters/ magazines, advertise our study via their social media channels (such as Twitter or Facebook), and also place our advertisement on noticeboards within physical spaces they use.

Some participants may be recruited by 'word of mouth', by which we mean they may contact us having heard about our research in conversation with a previous participant or other person, or following a conversation with a member of our research team, or through media coverage.

We will provide study information to anyone expressing an interest in participating. Further information about the study will also be available on our website. We will only be able to enrol participants who are eligible for the study. Should volunteers express a desire to participate, they will undergo the screening and eligibility assessment outlined below.

6.1. Screening and Eligibility Assessment

When a person who stutters contacts the research team and expresses a desire to participate, they will be sent the PIS outlining the procedures and risks involved in taking part. Screening will take place before volunteers have consented to take part in the study. The screening procedure involves obtaining information in line with tDCS, TMS, and MRI safety guidelines (outlined in the standard operating procedure documents developed within the Medical Sciences Division). Also see exclusion criteria in section 6.3 of this protocol. Screening criteria will be assessed by self-report.

Volunteers will also complete a screening assessment of stuttering severity to ascertain eligibility. In the first instance, one of the named investigators will conduct a screening by videoconference (Skype) to determine severity. Stuttering symptoms are typically increased on the first meeting (when participants are unfamiliar with their conversation partner) and over the telephone/ during videoconferencing. Consequently, if stuttering is determined to be of mild severity at this stage, the volunteer will be informed that they do not meet the inclusionary criteria for the study. If stuttering is of mild-moderate or greater severity, a face-to-face appointment will be scheduled, which will take place on University premises, or at the participant's home or office. The severity of stammering as ascertained on this visit will be used to determine whether participants should be enrolled into the study. If stuttering is of mild-moderate or greater severity, then they will be invited to participate.

Once we have determined eligibility, informed consent will be obtained and a suitable appointment will be scheduled, within three months of the screening. If the participant is deemed ineligible, we will first enquire if they wish to participate in other studies within the lab for which they might be eligible. If they do not, all screening data will be deleted (within a month of notification of ineligibility).

6.2. Informed Consent

The participant must personally sign and date the latest approved version of the Informed Consent form before any study specific procedures are performed.

Written and verbal versions of the Participant Information and Informed Consent will be presented to the participants detailing no less than: the exact nature of the study; what it will involve for the participant; the implications and constraints of the protocol; the known side effects and any risks involved in taking part. It will be clearly stated that the participant is free to withdraw from the study at any time for any reason without prejudice to future care, and with no obligation to give the reason for withdrawal.

The participant will be allowed as much time as wished to consider the information, and the opportunity to question the Investigator, their GP or other independent parties to decide whether they will participate in the study. Written Informed Consent will then be obtained by means of participant dated signature and dated signature of the person who presented and obtained the Informed Consent. The person who obtained the consent must be suitably qualified and experienced, and have been delegated responsibility by the Chief Investigator. A copy of the signed Informed Consent will be given to the participant. The original signed form will be retained at the study site.

6.3. Randomisation, blinding and code-breaking

A 'minimisation' sampling procedure will be used, whereby participants' stuttering severity as measured during screening with the SSI-4 will be used to assign successive participants to true stimulation or sham stimulation, minimising group differences in severity. A member of the Departmental of Experimental Psychology who is not involved with the study will be in charge of communicating to the project team what code they should use.

On the basis of this randomisation, half the participants will receive true tDCS stimulation and the other half will be in a control group that will not receive stimulation (sham tDCS). In sham tDCS the current is applied for a sufficiently brief duration to avoid any change in cortical

excitability (up to 30 seconds) but long enough to produce the transitory sensation on the skin associated with real tDCS. Although the stimulation is different, each participant will receive exactly the same speech training throughout the study.

The study will also be double-blinded, meaning that the researchers, study staff, and participants will not know whether the condition involves real or sham tDCS. The stimulator used in the study has a 'study' mode to allow the operator to be blind to the stimulation condition.

The person in charge of the randomisation procedure will have the capacity to unblind the data for analysis once data collection is complete. Data may be unblinded during the data collection only in the context of a serious adverse event potentially related to the type of stimulation or if a patient withdraws from the study and needs to be replaced.

6.4. Baseline Assessments

Following the screening to determine eligibility, participants will complete the baseline assessments (Visit 1, Days 1-2). This visit will take place at OHBA.

During this visit, we will obtain informed consent. We will obtain behavioural measures of speech fluency, as well as complete clinical assessments (SSI-4, OASES). Following this, participants will complete the brain and vocal tract imaging assessments (MRI and TMS) as described below.

6.5. Subsequent Visits

Visits 2-6 [Days 3-7]

These visits may take place at University testing facilities, or at the participant's home or office and will take place at the same time on each day. Participants will complete a short speech fluency assessment during reading and conversation at the start and end of the session; this assessment will be video recorded. A safety screening for tDCS will be conducted to ensure that the participant is not experiencing any discomfort/ risk, and to check that eligibility has not been compromised (for example, by use of medication). The intervention will then be delivered (sham vs. true tDCS + speech fluency training). The speech fluency training lasts approximately 40 minutes and stimulation is delivered for 20 minutes at the start of the training. Each session should last no more than one hour on each of the five days of intervention.

Visit 7 [Days 14-15]:

This visit will take place at OHBA. We will obtain behavioural measures of speech fluency, as well as complete clinical assessments (SSI-4). Following this, participants will repeat the brain and vocal tract imaging assessments (MRI and TMS) described. Standard operating procedures and safety guidelines for each of these procedures will be followed.

Visit 8 [+6 weeks following Visit 6]

This visit will be conducted via videoconference. We will obtain behavioural measures of speech fluency, as well as complete clinical assessments (SSI-4, OASES).

Visit 9 [+3 months following Visit 6]

This visit will be conducted via videoconference. We will obtain behavioural measures of speech fluency, as well as complete clinical assessments (SSI-4, OASES).

6.6. Description of procedures

Brain stimulation intervention [over 5 days]

tDCS

Once contraindications to transcranial direct current stimulation (tDCS) are excluded, the risks of taking part in a tDCS study are minimal. An experienced researcher will go through a list of possible risks with the participant before the study and answer any questions. TDCS directly and non-invasively stimulates the brain through the application of electrical currents to a small region of the scalp. The current is generated by a battery-powered stimulator and passed through rubber electrodes and conductive material (gel or saline-soaked sponges). At least one electrode is attached to the scalp with a band. The other electrode may be positioned on the scalp also or on the body (e.g. shoulder). The electrode size of the stimulators in use by research groups at present is large (~25-35 cm²) and the current strengths used are low (~1-3 mA) resulting in very low current densities (0.029 - 0.12 mA/cm²). The possible minor side-effects of tingling, itching or a mild burning sensation under the electrode are more likely with the higher current densities so are less desirable. Typical protocols apply no more than 20 minutes of stimulation in a single session. During the whole duration of the experiment, the participant is able to talk with the researchers and indicate any discomfort. The participant will be assured that they can withdraw from the study for any reason without penalty. In this study, we will use tDCS with 35 cm² electrodes placed over the frontal cortex bilaterally (channels FC5 and 6 electroencephalography). A 1-mA current will be used, ramped up over 30 seconds and applied for 20 minutes at the start of the speech fluency training. For the sham stimulation, the stimulator will ramp up the current to 1 mA over 30 seconds and then turned off. In study mode, the stimulator continues to test the impedance of the electrodes. This ensures that the researcher and the participant remain blind to stimulation condition.

Speech fluency assessments [All visits]

Participants will complete a reading and conversation task on each of the visits. These will be video- and audio-recorded, and scored offline by members of the investigation team for instances of dysfluency.

Brain and vocal tract assessments [at baseline and at follow up one week after training]

Brain stimulation techniques

TMS

TMS is a technique that allows us to stimulate the brain by rapid switching of a magnetic field in a coil placed over the head. Once contraindications to TMS are excluded, the risks of taking part in a TMS study are minimal. An experienced researcher will go through a list of possible risks with the participant before the study and answer any questions. The effects of TMS can be assessed by recording the activity of muscles (electromyography; EMG). EMG activity of the

muscle is measured at the surface of the skin by attaching an electrode (small silver disc). In order to record this activity, several electrodes will be taped on the skin over muscles of a participants' hands and lips. During TMS, a coil is positioned over the scalp and single pulses are used to stimulate the brain. The intensity of stimulation is varied until the EMG recording consistently shows activity in the muscle in response to the stimulation. Once the minimum intensity at which this activity is observed is determined, the experiment begins. We will use single pulses (suprathreshold) of TMS to measure the excitability of the motor cortex during speech perception and to assess interhemispheric connectivity. During the experiment, which would last no more than one hour, the participant is able to talk with the researchers and indicate any discomfort. The participant will be assured that they can withdraw from the study for any reason without penalty.

Imaging techniques

MRI

Imaging interventions: Once contraindications to magnetic resonance imaging are excluded by use of the facility's screening forms, the risks of undergoing a scan are minimal. A trained scanner operator or radiographer will go through a list of possible risks with the participant before scanning. The MRI scanner consists of a large powerful magnet. Magnetic resonance imaging uses no ionising radiation. There are, however, potential hazards associated with MRI and the scanning of participants including the presence of surgical implants, participants' clothing, jewellery (such as body piercings), or medical conditions. A comprehensive list of potential risks has been compiled, and the participant should be checked against this by the operator, prior to entering the controlled areas of the MRI scanners. During the actual scanning procedure, the scanner produces loud banging noises and the participant will be given suitable hearing protection (earplugs). There is a small mirror that will allow them to see out of the scanner. During the experiment, the participant will be able to communicate with the operator in the control room. In addition, they will be given a call button, which allows them to alert the operator at any time. People with a history of claustrophobia may be excluded from participation in the study. All participants will still be introduced carefully to the scanner and allowed to leave at any stage, should they wish to do so. Once in the scanner, participants will be able to indicate immediately if they wish the scanning to cease by pressing a call button in their hands.

The MRI session will last 90 minutes and participants will be allowed to come out of the scanner for a break if needed. Participants will be asked to lie still but remain awake during resting state scans. During structural image acquisition, they may watch a video of their choice or listen to music or radio. For the functional tasks, they will be given instructions and have the opportunity to practise the tasks outside the scanner to be sure that they understand what is required. Tasks will be simple and involve making button presses or speech responses to stimuli and listening to sounds. During the vocal tract imaging, participants will be asked to repeat words, non-words, and sentences. They will hear themselves speaking via headphones and sometimes this feedback will be altered.

Discontinuation/Withdrawal of Participants from Study

Each participant has the right to withdraw from the study at any time. In addition, the Investigator may discontinue a participant from the study at any time if the Investigator considers it necessary for any reason including:

- Ineligibility (either arising during the study or retrospectively having been overlooked at screening)
- Significant protocol deviation
- Significant non-compliance with treatment regimen or study requirements
- Withdrawal of Consent
- Loss to follow up

The reason for withdrawal will be recorded in the Case Report Form. We will replace participants who withdraw from the study, if we are able to do so. With permission, we will use the data of subjects who have withdrawn from the study, if it is usable (e.g. we may use behavioural, neural, or vocal data data that was collected until participant withdrew to evaluate our tertiary objectives). If we do not have the participants' permission to use the data, we will exclude it from our analyses, and all data and information collected from those participants will be securely destroyed.

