9.3. Analysis of Outcome Measures

Only data from participants who have not withdrawn consent will be included in final analyses. If participants drop out, we will attempt to replace their participation.

We will compare measures of speech function based on standardized tests and measures of speech fluency from speech samples. The primary outcome is defined as change in SSI-4 score (baseline subtracted), and the secondary outcomes are change in % disfluency and OASES score.

Differences between sham and tDCS intervention in brain imaging measurements will be evaluated using standardized analysis tools in the FMRIB Software Library. In functional MRI our outcome measures are the intensity and size of activation clusters based on the recorded blood-oxygenation-level-dependent signal (BOLD) that are involved in the tasks we ask participants to complete. Structural image analysis will be employed to measure white matter diffusion and grey matter morphometric differences in areas identified as abnormal in previous studies of stuttering.

Vocal tract imaging data will be analysed using custom tools to calculate the range of positions in tongue blade movement, lip protrusion, and laryngeal lowering during speech production. We predict that spatiotemporal variability in these movements will be greater in PWS compared with controls and reduce in those with measureable improvements in fluency following speech training.

The motor excitability and measures of cortical connectivity obtained using TMS and MEPs will be compared in PWS and Controls and at baseline relative to week 1 to examine for correlates of improved speech fluency in PWS.

We will compare differences in brain and vocal tract imaging data in PWS and controls. Only data from the baseline time point will be used.

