Study Title: Investigating Non-invasive brain Stimulation To Enhance fluency in People who stutter

Short title: INSTEP Trial
University of Oxford, Medical Sciences Division
IDREC Ethics Ref: R52173/RE001

Document title: INSTEP trial statistical analysis plan
Date and Version No: 23rd October 2017, version 1.0

Chief Investigator: [name], Department of Experimental Psychology, University of Oxford

Investigators: [name], Department of Experimental Psychology, University of Oxford

[name], Department of Experimental Psychology, University of Oxford

[name], Department of Experimental Psychology, University of Oxford

All the investigators declare that there are no conflicts of interest associated with the proposed study.

INSTEP trial statistical analysis plan

We plan to carry out analyses on the 'intention to treat' sample, i.e. including all participants who complete the study. If any participant has data that are group outliers, we will also complete sensitivity analyses (Thabane et al., 2013) by re-running all analyses excluding the relevant participant(s), to evaluate the robustness of the treatment effect. Speech data in people who stutter tends to significantly deviate from a normal distribution. Transformation of these data is problematic for reporting confidence intervals in interpretable units, therefore we will use change scores (baseline subtracted) in the analyses to overcome this limitation. For consistency, we will use this approach of baseline subtraction and analysis of change scores in analysis of other variables even if they do not suffer from the same skewness as the speech data. Variables that are not normally distributed will be analysed using nonparametric methods.

Primary outcome measure

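### The investigator may remove a participant from the whole study for non-compliance, deviation or ineligibility; nothing secures SSI-4 follow-up after an early stop, and the SAP analyses completers

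*Protocol*

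**What the plan says.** **Discontinuation.** The discontinuation and withdrawal text at the end of Protocol 6.6 states that "the Investigator may discontinue a participant from the study at any time if the Investigator considers it necessary for any reason including" five listed grounds. Three matter here: significant protocol deviation, "Significant non-compliance with treatment regimen or study requirements", and "Ineligibility (either arising during the study or retrospectively having been overlooked at screening". What ends is participation in the study, not one procedure.

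**What follows.** The reason is recorded. On replacement, Protocol 6.6 says "We will replace participants who withdraw from the study, if we are able to do so" and Protocol 9.3 says "If participants drop out, we will attempt to replace their participation". These sentences speak of withdrawing and dropping out; they plausibly, but not expressly, cover removal by the investigator. On data already held, Protocol 6.6 says "With permission, we will use the data of subjects who have withdrawn from the study, if it is usable"; its example is data gathered up to withdrawal, used for tertiary objectives.

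**Who is analysed.** Protocol 9.3: "Only data from participants who have not withdrawn consent will be included in final analyses". The SAP's opening paragraph labels its sample intention to treat and explains this as "including all participants who complete the study".

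**Scheduled follow-up.** Protocol 6.5 and Appendix B place SSI-4 at Visits 7, 8 and 9 (1 week, 6 weeks and 3 months after training). Visits 8 and 9 are held by videoconference. Neither place says what happens to someone who stops tDCS or training before the fifth session.

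**The concern.** Non-compliance, deviations and newly arising ineligibility occur after randomisation and may be related to fluency. If they end follow-up, the two arms being compared are no longer the arms that were randomised. Replacement restores the number of participants but not the randomised comparison.

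A concrete route exists. Before tDCS at Visits 2 to 6, Protocol 6.5 re-checks eligibility and gives medication use as an example. It states no consequence, so a man who fails the check might only miss that session. Protocol 6.6 also permits his removal as ineligible, and then nothing secures his three SSI-4 scores. New medication may be a reason to withhold current, but it is no reason to cancel a speech assessment by video.

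The two analysis rules disagree about such a man: he is outside the SAP's completer set, but inside the Protocol 9.3 set if he has not withdrawn consent. Even the wider rule cannot supply scores that were never collected, and the SAP gives no missing-data method. Its only sensitivity analysis is for outliers.

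**Working it through.** **Inputs from the documents.** 20 per arm, effect size 0.9, 80% power, 5% false-positive rate, and earlier effects of 0.93 (1 week) and 0.50 (6 weeks): Protocol 9.2. Equal allocation: Protocol 6.3. Primary outcome, SSI-4 change at three time points: SAP, Primary outcome measure.

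**Assumed inputs.** Losses per arm (k1 and k0) and the deficit d, in SD, of those lost relative to those kept. The documents give no discontinuation rate. I take 1 to 3 losses and d from 0.5 to 1.0; 3 of 20 is high for a five-day training period.

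**Step 1. The plan's own figure.** The normal approximation for an effect of 0.9, two-sided 5% and 80% power gives 20 per arm (power 81.2%). A two-sample t test at 20 per arm has power 79.2%. The stated size reproduces, and this point does not depend on it. There is little slack, however: with 18 per arm and no replacement, t-test power is 74.6%.

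**Step 2. Shift in the group contrast.** Shift = (k1 − k0)/20 × d.

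- One lost from one arm, d = 0.5: 1/20 × 0.5 = 0.025 SD. That is 0.025/0.93 = 2.7% of the 1-week effect and 0.025/0.50 = 5% of the 6-week effect.
- Three lost from one arm, d = 1.0: 3/20 × 1.0 = 0.15 SD, or 16.1% and 30%.
- Three against one: 2/20 × d = 0.05 to 0.10 SD.
- Equal losses of similar participants: 0.

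**Step 3. False-positive rate at one time point.** Two-sided 5% t test, no true effect, losses replaced so that the comparison is 20 against 20 (df 38). SE = √(2/20) = 0.316 SD; noncentrality = shift/SE.

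| Shift (SD) | Noncentrality | Rate |
|---|---|---|
| 0 | 0 | 5% |
| 0.025 | 0.079 | 5.07% |
| 0.05 | 0.158 | 5.27% |
| 0.10 | 0.316 | 6.10% |
| 0.15 | 0.474 | 7.48% |

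If the three are not replaced (17 against 20, df 35), SE = √(1/17 + 1/20) = 0.330, noncentrality = 0.15/0.330 = 0.455, and the rate is 7.27%.

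**Step 4. Group effect averaged over three time points.** Assume the same 0.15 SD shift at each and a correlation r between them. The SD of the mean is √((1 + 2r)/3).

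- r = 0.5: SD 0.816, noncentrality 0.581, rate 8.75%.
- r = 0.9: SD 0.966, noncentrality 0.491, rate 7.66%.

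**Step 5. Would a wider analysis set be enough?** The SAP specifies a mixed ANOVA with time as a within-subject factor. In its conventional form this needs all three scores, so someone with one or two would still be dropped. The model has to change along with the analysis set.

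**The case against.** The other side has a good deal of force.

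- A reader might infer that SSI-4 is not measured once training stops. That is wrong: Protocol 6.5, Appendix B and the SAP all schedule it after training. The gap concerns only participants who stop early.
- A reader might infer that missing a session ends participation. Nothing says so. Removal is discretionary, and Visits 7 to 9 are not made conditional on sessions received. Someone who missed a session but attended those visits can be read as having completed the study, and so stays in the SAP sample.
- Poor tolerability is not a listed ground. It could enter only through the open-ended wording or through non-compliance. Ineligibility overlooked at screening concerns a fact that predates randomisation, so it is a weak example of post-randomisation selection.
- Balanced losses are plausible. Training is identical in both arms, the current is 1 mA for 20 minutes, treatment lasts five days, medication and contraindications are screened beforehand, and staff and participants are blinded.
- The 1-week visit is at the imaging centre alongside MRI and TMS, so it is more than a video call.

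All of this stands and limits the size of the point. It does not close the gap. Blinding prevents removal being chosen by arm, but compliance could still differ between real and sham current. Discretion leaves follow-up permitted but not secured. The conflict between the SAP and Protocol 9.3 remains whatever the loss rate.

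**Conclusion.** The point holds in a limited form. The investigator may, but need not, remove a participant from the whole study on grounds that mostly arise after randomisation. SSI-4 is not secured for anyone who stops early, and the SAP's completer set conflicts with Protocol 9.3.

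The documents do not support saying that the trial is biased or that removal will be frequent. Under the assumed one-arm losses, the false-positive rate at a single time point is about 5.1% to 7.5%. Losses of three against one give 5.3% to 6.1%, and balanced, similar losses leave it at 5%. The three-time-point figures of 7.7% and 8.7% also need the worst-case shift at every visit. All these figures rest on assumed counts and deficits.

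An amendment is still justified, because it is cheap and scores that were not collected cannot be recovered by any later analysis.

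**What to change.** 1. **Protocol 6.6, discontinuation text.** State that non-compliance, protocol deviation or ineligibility may end tDCS and training, or MRI and TMS, but not follow-up. Unless the participant declines, SSI-4, percentage disfluency, BAI, PAiS and the severity and naturalness ratings continue at 1 week, 6 weeks and 3 months, and OASES at 6 weeks and 3 months only. If MRI and TMS have stopped, the 1-week assessment may be done live at home or office plus videoconference; Protocol section 4 already allows researchers to travel for live components. A participant still in follow-up is not replaced. When to stop stimulation stays with the investigator.
2. **SAP, opening paragraph.** Replace the completer definition with all randomised participants who have at least one post-baseline score and consent to use of their data, analysed in their allocated arm regardless of sessions received. This also brings it into line with Protocol 9.3.
3. **SAP, Primary outcome measure.** Fit the group-by-time analysis as a likelihood-based mixed model for repeated measures, so that participants with one or two follow-up scores are retained.

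The cost is a short amendment to both documents and a few assessments already in the schedule. The downside is that the estimate will include partly treated participants and may be slightly smaller.
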